4.5.3. Adverse Event Assessment

At each study visit following the receipt of first dose of study drug and continuing through four weeks following the final dose of study drug, the study participant will be assessed for any AEs.

An AE is any unfavorable and unintended sign (including an abnormal laboratory finding), symptom, or disease temporally associated with the use of medicinal (investigational) product whether or not considered drug related. The occurrence of an AE may come to the attention of study personnel during study visits and interviews of a study participant presenting for medical care, or upon review by a study monitor.

Information to be collected on reportable AEs includes event description, time of onset, clinician's assessment of severity, relationship to study product (assessed only by those with the training and authority to make a diagnosis, which would include MD or DO), and time of resolution/stabilization of the event. All AEs occurring from Study Day 1 through four weeks following the last dose of study drug must be documented appropriately regardless of relationship. All AEs will be followed to adequate resolution.

Any medical condition that is present at the time that the patient is enrolled should be considered as a baseline condition and not reported as an AE. However, if the event meets the criteria and the grade of the event worsens at any time during the study, it should be recorded as an AE.

The determination of seriousness, severity, and causality will be made by an on-site investigator who is qualified (licensed) to diagnose AE information, provide a medical evaluation of AEs, and classify AEs based upon medical judgment. This includes MD or DO. Events will be identified by assessing the participant at each visit. If a participant is hospitalized, the medical record should be reviewed to identify AEs. The PI is responsible for identifying and reporting AEs according to protocol guidelines.

Unsolicited AEs

All AEs spontaneously reported by the participant and/or in response to an open question from study personnel or revealed by observation, physical examination or other diagnostic procedures must be recorded in the source document and on the appropriate page of the CRF. All reported unsolicited AEs are graded in accordance with the toxicity tables ([Table 5](#) and [Table 6](#)).

Serious AEs

An SAE is defined as an AE or suspected AE is considered "serious" if, in the view of either the investigator or sponsor, it results in any of the following outcomes:

- Death,
- A life-threatening adverse event*;
- Inpatient hospitalization or prolongation of existing hospitalization;
- A persistent or significant incapacity or substantial disruption of the ability to conduct normal life functions; or
- A congenital anomaly/birth defect.

* Life-threatening AE. An AE is considered "life-threatening" if, in the view of either the investigator or sponsor, its occurrence places the patient or participant at immediate risk of death. It does not include an AE that, had it occurred in a more severe form, might have caused death. It does not necessarily include all grade 4 AEs according to the toxicity tables ([Table 5](#) and [Table 6](#)).

Important medical events that may not result in death, be life-threatening, or require hospitalizations may be considered serious when, based upon appropriate medical judgment they may jeopardize the patient or participant and may require medical or surgical intervention to prevent one of the outcomes listed in this definition. Examples of such medical events include allergic bronchospasm requiring intensive treatment in an emergency room or at home, blood dyscrasias or convulsions that do not result in inpatient hospitalization, or the development of drug dependency or drug abuse.

Severity of AE

All reportable AEs will be graded by the investigator according to the protocol toxicity tables ([Table 5](#) and [Table 6](#)) using a four-grade system: Mild, Moderate, Severe, and Potentially Life-Threatening. For safety laboratory results with an absolute number in the toxicity tables (e.g., hemoglobin), grading of the AEs will be according to the toxicity tables and not according to the local laboratory reference range. For safety laboratory results with a reference to the Upper Limit of Normal (ULN) in the toxicity tables (e.g., ALT or SGPT), grading of the AEs will utilize the ULN of the local laboratory reference range in determining grading of the event per the toxicity tables. Grade 4 AEs will be only reported as SAE if the event meets one of the regulatory definitions of SAE described below based on the study site physician judgment. The functional table below should be used to grade the severity of an AE that is not specifically identified in the grading table.

In addition, all deaths related to an AE are to be classified as grade 5.

Relationship to Study Intervention

For each reported adverse reaction, the Principal Investigator (PI) or designee must assess the relationship of the event to the study product using the following guideline:

- **Related** – The AE is known to occur with the study intervention, there is a reasonable possibility that the study intervention caused the AE, or there is a temporal relationship between the study intervention and event. Reasonable possibility means that there is evidence to suggest a causal relationship between the study intervention and the AE.
- **Not Related** – There is not a reasonable possibility that the administration of the study intervention caused the event, there is no temporal relationship between the study intervention and event onset, or an alternate etiology has been established.

Time Period and Frequency for AE Assessment and Follow-up

All AEs, including safety laboratory AEs, and all SAEs will be documented from Study Day 1 through four weeks following the last dose of study drug.

All AEs and SAEs will be followed until resolution, even if this extends beyond the study-reporting period, which is 4 weeks following the last dose of study product. Resolution of an AE is defined as the return to pretreatment status or stabilization of the condition with the expectation that it will remain chronic.

At any time after completion of the study, if the investigator becomes aware of an SAE that is suspected to be related to study product, the investigator will report the event.

4.5.4. Concomitant Medications Assessment

At each study visit from the receipt of first dose of study drug and continuing through four weeks following the final dose of study drug, concomitant medications that are being administered to the participant will be recorded.

4.5.5. Laboratory Evaluations

Blood for study-specified laboratory evaluations may be obtained by methods such as the following: venipuncture, heel stick, indwelling intravenous catheter, etc. As detailed below, blood will be obtained for assessment of hematology safety labs, chemistry safety labs, and acyclovir concentrations; blood draws will be attempted a second time if the first attempt is unsuccessful. If an insufficient volume of blood is obtained for all of the tests at any given study visit, the following prioritization as to which tests to send will apply (most important to least important): 1) PK samples for acyclovir plasma concentrations (most important); 2) hematology safety labs (second most important); and 3) chemistry safety labs (third most important). With the exception of the PK samples and the WBC count with differential, those lab tests that are unable to be obtained due to lack of sufficient blood or parental refusal at a given study visit will be noted but will not be reported as protocol deviations. As far as possible, research specimens should be taken to coincide with clinical care.

If a laboratory value is outside of the protocol specified range, then the measurement may be repeated if there is a technical problem with the measurement caused by a laboratory error or a malfunctioning or inappropriate device. Laboratory parameters other than those specified in hematology safety labs and chemistry safety labs as part of the complete blood count and complete metabolic panel need to be evaluated by the site physician, recorded in the source document, and reported as laboratory AEs if clinically significant.

Clinical Laboratory Evaluations

Clinical laboratory results can be used for chemistry and hematology safety labs if collected within the required study window and will be graded according to [Table 6](#). If labs drawn for the study-required assessments are not evaluable, blood draws will not be repeated.

Hematology Safety Labs

All hematology safety laboratory assessments will be conducted at the PI's local lab. They will be obtained on Study Days 1 and 5. The following will be tested: WBC with differential, hemoglobin, and platelet count. From the WBC count and differential, the ANC will be calculated.

Chemistry Safety Labs

All chemistry safety laboratory assessments will be conducted at the PI's local lab. They will be obtained on Study Days 1 and 5. The following will be tested: ALT and creatinine.

5. SAMPLE SIZE CONSIDERATIONS

The sample size will be characterized by the width of a 95% confidence interval (CI) for AUC_{∞} in Cohort 1. As previously noted, in infants 1-2 months of age, the mean (\pm SD) AUC_{∞} is 36,000 (\pm 12,000) ngxhr/mL for a normalized dose of 10 mg/kg of intravenous (IV) acyclovir [8]. A higher (lower) dose for Cohort 2 will be considered when observed acyclovir exposures in Cohort 1 are below the mean of 24,000 (above 48,000) ngxhr/mL. Assuming a constant coefficient of variation of 0.3333 in determining the SD of AUC_{∞} for a given mean, a sample size of eight will be characterized in terms of the width of a 95% two-sided CI for the mean. If the observed mean is 24,000 ngxhr/mL and using a SD of 8,000 ngxhr/mL, a two-sided 95% CI for the mean AUC_{∞} is (17,312-30,688), i.e., the true mean can be as low as 17,312 ngxhr/mL but no higher than 30,688 ngxhr/mL. If the observed mean is 48,000 ngxhr/mL and using a SD of 15,998 ngxhr/mL, a two-sided 95% CI for the mean AUC_{∞} is (34,625-61,375), i.e., the true mean can be as high as 61,375 ngxhr/mL but no lower than 34,625 ngxhr/mL. For the CIs for other sample sizes, refer to [Table 3](#).

For the 95% upper bound for the proportion experiencing AEs or SAEs when 0 are observed in a sample size of n . For example, if $n=8$ and no SAEs are observed, then there is 95% confidence that the rate is no more than 36.9%. If $n=10$, there is 95% confidence that the rate is not more than 30.8%. The larger the n , the tighter (i.e., closer to 0) the upper bound.

6. GENERAL STATISTICAL CONSIDERATIONS

6.1. General Principles

In general, all data will be listed, sorted by site, dose level, and participant, and when appropriate by visit within participant. All summary tables will be structured with columns for dose level (10 mg/kg, 20 mg/kg) and will be annotated with the total population size relevant to that table/treatment, including any missing observations.

All continuous variables will be summarized using the following descriptive statistics: n (non-missing sample size), mean, SD, median, maximum, and minimum. For laboratory data, 10th and 90th percentiles will be used instead of minimum and maximum. The frequency and percentages (based on the non-missing sample size) of observed levels will be reported for all categorical measures.

Boxplots will be used to display change from baseline summary statistics for continuous variables. For estimating proportion CIs, the Clopper-Pearson method will be utilized, where the confidence level will be at least 95% for estimation.

6.2. Timing of Analyses

The final analyses of safety data will be performed after database lock.

6.3. Analysis Populations

6.3.1. ITT Population

Any child who receives at least one dose of study medication will be included in an ITT analysis of safety.

6.3.2. Safety Population

The Safety Population will consist of all participants who have received at least one dose of study product and for whom any data on safety are available.

6.3.3. Per Protocol Population

The Per Protocol Population will consist of all participants who complete the course of study medication. A complete dose of study medication includes having received 7, 8, 9, or 10 doses.

6.3.4. PK Population

The PK Population will be defined in a separate PK analysis plan.

6.4. Covariates and Subgroups

The protocol does not define any formal subgroup analyses, and the study is not adequately powered to perform subgroup analyses.

6.5. Missing Data

Missing safety data will be assumed to be missing completely at random and will not be imputed.

6.6. Interim Analyses and Data Monitoring

The initial oral valacyclovir dose will be 10 mg/kg administered two times daily for 5 days (Cohort 1). The target exposure for acyclovir following oral valacyclovir dosing is 36,000 ngxhr/mL with a range of 24,000 ngxhr/mL to 48,000 ngxhr/mL. Upon full accrual and follow-up of Cohort 1, the PK and safety data will be reviewed by the SMC, using the approved report shell. If the mean of observed acyclovir exposures of participants in Cohort 1 are below 24,000 ngxhr/mL, AND if no Grade 3 or Grade 4 AEs or SAEs are detected in any of the study participants, then the participants enrolled in Cohort 2 will receive oral valacyclovir at a dose of 20 mg/kg administered two times daily for 5 days. Alternatively, if the mean of observed acyclovir exposures of participants in Cohort 1 are above 48,000 ngxhr/mL AND if no Grade 3 or Grade 4 AEs or SAEs are detected in any of the study participants, then the participants enrolled in Cohort 2 will receive oral valacyclovir at a dose that has been linearly adjusted downward to target 36,000 ngxh/mL AUC₁₂. The SMC retains the ability to suggest an alternative dose be studied in Cohort 2 if the mean AUC₁₂ from Cohort 1 is within but at or near the lower or upper ranges in order to attain an AUC₁₂ closer to the 36,000 ngxhr/mL target. Based on review of the safety and PK data by the SMC after Cohort 1, it was decided that Cohort 2 would be opened for enrollment and those participants would receive oral valacyclovir at a dose of 20 mg/kg administered two times daily for 5 days.

If the targeted exposure is not achieved in Cohorts 1 and 2 and the safety data are acceptable, it is possible, but not anticipated, that additional dosing cohorts could be recommended based upon the results of participants in the first two cohorts. If such a recommendation is made, dose selection and participant enrollment and assessment will follow the approach used for Cohort 2.

The SMC will also conduct ad hoc meetings if trial-level halting criteria are met or at the request of DMID to review a potential safety concern identified by either the lead PI, DMID Medical Monitor, or protocol team. Additional data may be requested by the SMC, and interim statistical reports may be generated as deemed necessary and appropriate by the SMC.

There are no other planned interim analyses.

6.7. Multicenter Studies

Data will be pooled across all clinical sites. Center effects are not anticipated because the sites are using standardized procedures for product administration and assessment of unsolicited AEs, and the study relies on central laboratories for the assessment of PK endpoints.

6.8. Multiple Comparisons/Multiplicity

No adjustments for multiple testing are planned.

7. STUDY PARTICIPANTS

7.1. Disposition of Participants

The disposition of participants in the study will be tabulated by dose level, providing summaries of the disposition metrics noted in Section 4.5.1 (Table 7). The composition of analysis populations, including reasons for participant exclusion, by dose level, will also be summarized (Table 8). Reasons participants were screened but not enrolled will be summarized (Table 9).

A flowchart showing the disposition of study participants, adapted from the Consort Statement will be generated (Figure 1). This figure will present the number of participants screened, enrolled, lost to follow-up, and analyzed, by dose level.

A listing of participants who received study product will be generated (Listing 1). Participants who terminated early and/or discontinued study product will be listed (Listing 2). A listing of participants excluded from analyses will be generated (Listing 5).

7.2. Protocol Deviations

A summary of participant-specific protocol deviations will be presented by the reason for the deviation, the deviation category, and dose level for all participants (Table 4). This table will provide the number of participants and the number of deviations for each deviation and deviation type. All participant-specific protocol deviations and non-participant specific protocol deviations will be included in participant listings (Listing 3 and Listing 4, respectively).

All protocol deviations will be classified as either a major or minor deviation and summarized accordingly. As the question of a major or minor deviation was not included on the protocol deviation CRFs, the following process will be used to classify the deviations: (1) Prior to database lock, the SDCC will generate a spreadsheet of all protocol deviations (participant-specific and non-participant specific separately) and will assign major/minor according to the major protocol deviation list finalized with DMID; (2) DMID will review the list and confirm the agreement or not; (3) Once the classifications are completed and finalized, the SDCC will incorporate this spreadsheet into their programming.

8. EFFICACY EVALUATION

There are no efficacy objectives/endpoints for this study.

9. SAFETY EVALUATION

9.1. Demographic and Other Baseline Characteristics

Summaries of the demographic and baseline characteristics noted in Section 4.5.2 will be summarized by study site ([Table 10](#) and [Table 11](#)) and dose level ([Table 12](#) and [Table 13](#)).

Individual participant listings will be generated for all demographic and growth parameters ([Listing 6](#)).

9.1.1. Prior and Concurrent Medical Conditions

All current illnesses and past pre-existing medical conditions will be coded using Medical Dictionary for Regulatory Activities (MedDRA) dictionary version 27.0 or higher.

Summaries of participants' pre-existing medical conditions will be presented by dose level ([Table 14](#)).

Individual participant listings will be generated for all medical conditions ([Listing 7](#)).

9.1.2. Prior and Concomitant Medications

Summaries of medications that were started prior to dosing and continuing at the time of dosing will be presented by WHO Drug Terms 2 and 3 and dose level ([Table 27](#)).

Individual participants listings will be generated for all concomitant medications ([Listing 11](#)).

9.2. Measurements of Treatment Compliance

A listing of the treatment compliance data noted in Section 4.4.8 will be generated ([Listing 8](#)).

Section 7.1 describes the additional tabular and listing output for compliance data.

9.3. Adverse Events

Safety evaluations will be based on the incidence, severity, and type of AEs. Safety variables will be tabulated and presented for all participants in the safety population.

When calculating the incidence of AEs (i.e., on a per participant basis), each participant will only be counted once and any repetitions of AEs within a participant will be ignored; the denominator will be the total population size. All AEs reported will be included in the summaries and analyses.

9.3.1. Unsolicited Adverse Events

An overall summary of unsolicited AEs will be generated which includes the following participant-level counts in each dose level: the number of participants reporting at least one AE, related AE, SAE, related SAE, and AE leading to early termination from the study ([Table 15](#)).

The number and percentage of participants reporting at least one unsolicited AE will be summarized by MedDRA System Organ Class (SOC) and Preferred Term (PT) (Table 16). The number of events within each SOC and PT will also be presented with the participant-level counts in this table. Counts and percentages will also be broken out by severity (Table 17). Related AEs will be summarized similarly (Table 18). Tabular summaries will be supplemented by the following graphical summaries:

- Event-level counts of AEs by SOC and severity (Figure 2)
- Event-level counts of related AEs by SOC and severity (Figure 3)
- Participant-level counts of AEs by SOC and maximum severity (Figure 4)
- Participant-level counts of related AEs by SOC and maximum severity (Figure 5)

The following participant listings will be generated:

- Unsolicited AEs (Listing 9)
- SAEs (Table 19)
- Non-serious unsolicited AEs of moderate or greater severity (Table 20)

9.4. Deaths, Serious Adverse Events and other Significant Adverse Events

A participant listing of SAEs, including deaths, will be generated (Table 19).

9.5. Pregnancies

Not applicable.

9.6. Clinical Laboratory Evaluations

Laboratory results will be summarized separately for chemistry and hematology parameters. Laboratory data summaries will include:

- Results by time point and severity (Table 23 and Table 25).
- Descriptive statistics including mean, SD, and change from baseline by time point (Table 24 and Table 26)
- Graphical summary of the change from baseline (Figure 6 and Figure 7)

Participant listings of clinical laboratory results will be generated for abnormal values, including results that are outside the normal range, (Table 21 and Table 22) and all values (Listing 10 and Listing 11).

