informed consent, each subject will receive 10 mg/kg of oral valacyclovir, and may start taking oral valacyclovir while still in the birth hospital, with subsequent dosing at home, or may start taking oral valacyclovir following discharge from the birth hospital. **Study Day 1** is the day that the first dose of oral valacyclovir is administered. Following signing of informed consent but prior to administration of the first dose of valacyclovir, hematology and chemistry safety labs (white blood cell count and differential for absolute neutrophil count, hemoglobin, platelet count, alanine aminotransferase, and creatinine) will be obtained and values checked; if no baseline hematology or chemistry values are Grade 1 toxicity or higher then dosing of valacyclovir will proceed; if any value is Grade 1 toxicity or higher, the subject will be withdrawn from the study prior to receiving any doses of study medication. In addition, the subject must have had a first void before receiving a first dose of study medication. A single plasma sample will also be obtained for a baseline acyclovir concentration, since the mothers of enrolled subjects will have been taking antiviral medication prior to delivery. Dropouts and withdrawn subjects may be replaced to reach the target sample size of eight subjects. Subjects will return to the study site on Study Day 5 (window: Study Day 4 through Study Day 5), and also will be assessed for adverse events and concomitant medications on Study Day 10 (window: Study Day 7 through Study Day 13) and on Study Day 42 (window: Study Day 35 through Study Day 49), although the Study Day 10 and 42 assessments may occur via telephone or in-person study visits. On the Study Day 5 (window: Study Day 4 through Study Day 5) visit, plasma samples for PK assessments will be obtained around dose 7, 8, 9, or 10 of study drug at 0 hour minus 15 minutes (pre-dose), and then 1-2 hours, 4-6 hours, and 8-10 hours following administration of the valacyclovir dose (full PK profile). Safety laboratory assessments (white blood cell count with differential, hemoglobin, platelet count, alanine aminotransferase, and creatinine) will be obtained at the Study Day 1 (baseline) and Study Day 5 visits. Safety laboratory values will be classified using the Division of AIDS Toxicity Tables ([Appendix A](#)). Study drug will be stopped following the obtaining of the PK samples on Study Day 5 (window: Study Day 4 through Study Day 5). Criteria for AEs or SAEs leading to halting of the study are detailed in [Section 7.1.1](#). The total number of study days of study drug administration will be 4 or 5 (depending on where in the window the Study Day 5 visit is conducted), although the total number of doses can be 7, 8, 9, or 10 depending upon when the study drug was started on Study Day 1 and whether the PK blood draws on Study Day 5 (window: Study Day 4 through Study Day 5) are around the first or second dose that day.

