5.1 Inclusion Criteria

To be eligible to participate in this study, an individual must meet all of the following criteria:

- Signed informed consent from parent(s) or legal guardian(s)
- Maternal history of genital HSV infection
- Maternal receipt of oral acyclovir, valacyclovir, or famciclovir suppressive therapy for ≥ 7 days prior to delivery
- Gestational age ≥ 38 weeks at birth
- ≤ 2 days of age at study enrollment*
- Weight at study enrollment $\geq 2,000$ grams

* For purposes of this study, the calendar day of birth is Day of Life 0

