3.3. Study Definitions and Derived Variables

Baseline Value

The baseline value will be defined as the last value obtained prior to the administration of study product.

Post-Baseline Value

Post-Baseline values refer to measurements and assessments collected after the first administration of study product.

Change From Baseline

Change from baseline will be calculated as: (Post-Baseline value) – (Baseline Value). If the baseline value is not available or is indeterminant, change from baseline will be undefined.

Analysis Day

For clinical laboratory data, summaries will be generated by nominal time point corresponding to the study visit day (e.g., Baseline and Day 5). For such summaries, the data point collected within the visit window (see [Table 2](#)) will be used as the data point for the time point. In the case of multiple records within a specific visit window, the value that is closest to the targeted study day will be used in the summaries. If observations have the same distance to the scheduled assessment, the latest one will be used. Data from supplemental and/or unscheduled visits may be used to provide a measurement for a time point, if appropriate.

All the recorded data will be included in listings.

Days on Study

The number of days the participant was on study will be calculated as follows:

(Protocol completion date or early termination date) – (Enrollment date) + 1

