
Notes: N = Number of participants in the Safety Population. n = Number of participants with data recorded at the respective time point. For the change from baseline, n represents the number of participants with non-missing data at baseline and the respective visit. SD = Standard Deviation.
										

14.3.5.2 Hematology Results**Table 25: Hematology Results by Parameter, Time Point, Severity, and Dose Level, Safety Population**

Similar shell as to Table 25. Parameters will be shown in the following order: Any Parameter, Absolute Neutrophil Count (ANC), Hemoglobin, Platelets, WBC.

Table 26: Hematology Summary Statistics by Parameter, Time Point, and Dose Level, Safety Population

Similar shell as to Table 26. Parameters will be shown in the following order: Absolute Neutrophil Count (ANC), Hemoglobin, Platelets, WBC.

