14.3.5 Displays of Laboratory Results

Figure 6: Chemistry Mean Changes from Baseline at Day 5 by Parameter and Dose Level, Safety Population

[Implementation Note: Each panel will be a separate parameter. Update “TBD” to “20 mg/kg”.]

Figures with similar format:

Figure 7: Hematology Mean Changes from Baseline at Day 5 by Parameter and Dose Level, Safety Population

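### ANC change from baseline is summarised by dose level without regard to age at the baseline draw, so an imbalance in baseline age can create or mask an apparent dose difference

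*SAP*

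**What the plan says.** SAP 9.6 asks for "Descriptive statistics including mean, SD, and change from baseline by time point", with hematology in Table 26. The note under the Table 26 shell reads "Parameters will be shown in the following order: Absolute Neutrophil Count (ANC), Hemoglobin, Platelets, WBC", so ANC comes first. Figure 7 is titled "Hematology Mean Changes from Baseline at Day 5 by Parameter and Dose Level, Safety Population". Neither display refers to age.

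Four other provisions determine what the change score contains:

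- **Age at entry.** Protocol 5.1 sets a maximum of "2 days of age at study enrollment" and adds "For purposes of this study, the calendar day of birth is Day of Life 0". A baseline can therefore be drawn at age 0, 1 or 2 days.
- **Baseline.** SAP 3.3: "The baseline value will be defined as the last value obtained prior to the administration of study product". Of the hematology labs, SAP 4.5.5 says "They will be obtained on Study Days 1 and 5".
- **Grading.** Protocol Appendix A and SAP Table 6 band ANC by age. Grade 1 is 4,000–5,000 cells/mm³ at ≤1 day and 1,250–1,500 at 2–7 days.
- **Pre-dose rule.** Protocol 4.1: "if any value is Grade 1 toxicity or higher, the subject will be withdrawn from the study".

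SAP 4.2 confirms that there is no comparator arm, and SAP 6.4 plans no subgroup analysis.

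**The concern.** Protocol 2.3.1 names neutropenia first among the toxicities of parenteral acyclovir in young infants. Table 26 and Figure 7 are where a reader will set ANC change at 10 mg/kg beside that at 20 mg/kg. Protocol 9.4.4 says graphics will help in comparing the dose cohorts, and 9.4.1 allows a mixed model of hematology change over time for the same purpose.

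The protocol's own grading limits treat a much lower ANC as unremarkable from age 2 days. The pre-dose rule carries that step into the baseline values of every dosed infant. A change score from a ≤1-day baseline therefore spans the step, and one from a 2-day baseline does not. With 8 infants per cohort, no comparator and no balancing on age, the average change depends on how many baselines were early as well as on the drug. An imbalance could look like dose-related neutropenia, or conceal it.

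**Working it through.** The documents give no figure for expected ANC change, so there is no planned number to reproduce.

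**1. Size of the step (Protocol Appendix A, cells/mm³).** Percentage drop = (limit at ≤1 day − limit at 2–7 days) / limit at ≤1 day.

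| Cut-off | ≤1 day | 2–7 days | Drop | % |
|---|---|---|---|---|
| Top of Grade 1 (ungraded above this) | 5,000 | 1,500 | 3,500 | 70.0 |
| Bottom of Grade 1 | 4,000 | 1,250 | 2,750 | 68.75 |
| Bottom of Grade 2 | 3,000 | 1,000 | 2,000 | 66.7 |
| Bottom of Grade 3 | 1,500 | 750 | 750 | 50.0 |

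The step is specific to ANC. WBC and hemoglobin each have one band through 7 days, and platelets have no age bands.

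**2. Which band each visit falls in.** The visit window is Study Day 4 or 5, which adds 3 or 4 days to the age on Study Day 1. This takes Study Day 1 as the enrolment day.

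| Age at baseline | Baseline band | Minimum ANC to be dosed | Age at Day 5 visit | Day 5 band |
|---|---|---|---|---|
| 0 days | ≤1 day | above 5,000 | 3–4 days | 2–7 days |
| 1 day | ≤1 day | above 5,000 | 4–5 days | 2–7 days |
| 2 days | 2–7 days | above 1,500 | 5–6 days | 2–7 days |

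An infant going from just above 5,000 to just above 1,500 is ungraded at both visits and contributes a change of about −3,500.

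**3. Effect on a cohort mean.** Assume no drug effect and that each infant tracks the ungraded limit. With k of 8 infants drawn at ≤1 day, the mean change is −3,500 × k / 8:

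- k = 1: −437.5
- k = 2: −875
- k = 8: −3,500

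The spurious difference between dose levels is 3,500 × (difference in k) / 8. For scale, Grades 1 to 3 at 2–7 days are each about 250 wide, so 875 equals 875 / 250 = 3.5 such bands.

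**4. How likely an imbalance is.** Assume each infant independently has probability p of a ≤1-day baseline, with 8 per cohort.

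| p | Differ by ≥1 | Differ by ≥2 | Differ by ≥3 |
|---|---|---|---|
| 0.3 | 0.784 | 0.411 | 0.169 |
| 0.5 | 0.804 | 0.454 | 0.210 |
| 0.7 | 0.784 | 0.411 | 0.169 |
| Spurious shift, at least | 437.5 | 875 | 1,312.5 |

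Check at p = 0.5: P(differ by ≥2) = 1 − [C(16,8) + 2·C(16,9)] / 2¹⁶ = 1 − (12,870 + 22,880) / 65,536 = 0.454.

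The probability that a single cohort contains baselines from both bands is 1 − p⁸ − (1 − p)⁸, which is 0.94 at p = 0.3 or 0.7 and 0.99 at p = 0.5.

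**The case against.** The strongest reply is that no stated decision uses mean ANC change. The safety endpoints are Grade 3 AEs, Grade 4 AEs and SAEs. Dose selection and halting also work from grades or SAEs, and ANC grades are age-banded. SAP 9.6 is descriptive. Table 26 follows a shell that already gives the value at each visit by dose level, SAP 6.1 specifies boxplots for change, and Listing 11 gives age at each study day. With about 16 infants, a careful reader could reconstruct the picture. All of this stands and limits the consequence to interpretation. It does not correct the change columns or Figure 7, which will be read by dose level.

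A second reply is that Appendix A holds toxicity cut-offs, not typical counts. This also stands. The cut-offs show that the protocol expects lower counts from day 2, but they do not measure the normal fall.

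Three stronger readings are tempting, and the documents do not support them:

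- *Day 5 always falls in a later age band than baseline.* This is untrue for 2-day baselines, which stay in the 2–7 day band. That contrast is what produces the confounding.
- *Every cohort will show a large ANC fall without any drug effect.* Actual ages are not given; eligibility only permits ≤1-day baselines. A cohort drawn mostly at 2 days would show little of this step.
- *The spurious difference will be several thousand cells.* Simulating lognormal counts with a CV of 40% and each limit at its 5th–10th percentile gives mean falls of about 6,500–7,400 for ≤1-day baselines. Neither document supplies that shape, spread or percentile. A 6-versus-2 split, or any gap of four or more infants, has a probability of only about 0.05–0.08 under the same 30–70% assumption.

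**Conclusion.** The point holds as a confounding problem in one descriptive display. The 3,500-cell (70%) step and its entry into baselines through the pre-dose rule follow directly from the documents. The placement of all Day 5 values in the 2–7 day band also requires dosing to start at enrolment.

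The effect on a cohort mean, about −440 per additional ≤1-day baseline, assumes that infants track the limit and that nothing further changes after day 2. The 0.41–0.45 probability of a gap of two or more infants, worth at least 875 cells/mm³ between dose levels, assumes that 30–70% of baselines are drawn at ≤1 day, independently across infants. These figures illustrate the mechanism and do not predict the result.

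The graded safety tables, endpoints, dose-selection rule and halting rules are not affected. The change is still worth making: it concerns the ANC rows for a toxicity the protocol names first, and the age needed is already collected.

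**What to change.** In SAP 9.6, for ANC only:

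1. In Table 26 and Figure 7, show change from baseline by age at the baseline draw (≤1 day; ≥2 days) within dose level. Use ≥2 days as the upper band because the age limit applies at enrolment and the first dose may follow hospital discharge.
2. Plot individual values in Figure 7, since some cells will be very small or empty.
3. Name the Day 5 ANC value, already in Table 26, as the main ANC comparison between dose levels. Dividing it by the age-band limit would add nothing: when dosing starts at enrolment, every Day 5 value would be divided by the same 1,500.
4. Footnote both displays: change from a ≤1-day baseline includes the age step and, without a comparator, cannot be attributed to the drug.

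The cost is a short SAP edit and one extra split in one table and one figure panel. It needs no new data and no change to study conduct. The drawback is small cells, in which SDs and 10th/90th percentiles will mean little, so the split should remain descriptive.
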